5.4 Safety Endpoints and Analyses

For all safety endpoints, the safety population (SP) will be used. Descriptive summary will be provided for safety endpoints.

The summarization of AEs will include only TEAEs (defined as AEs that begin or worsened on or after the date of first dose of double-blind IMP until 30 days after last dose of IMP). All TEAEs, SAEs, related AEs, Adverse events of special interest (AESIs) will be summarized by MedDRA SOC, severity and relationship to study drug for each treatment group. Fatal AE, AEs leading to discontinuation of IMP or study, will each be summarized by treatment group.

Clinical safety laboratories, including hematology, blood chemistry, coagulation (for subjects taking anti-coagulation medication only), glucose (by history of diabetics), and urinalysis; PE findings; vital signs; ECG readings; and weight will be summarized by the value and by change/percent change from baseline (where appropriate) at each protocol scheduled time point.

5.4.1 Adverse Events (AEs)

AEs will be coded using the latest version of MedDRA and preferred term PT. Patients with AEs that are ongoing at study completion or study withdrawal must be followed until resolution, until determined to be stable/chronic, or for 30 days after the last study visit, whichever comes first. Summary tables will focus on TEAEs; however, listings will include all AEs (with non-TEAEs flagged).

In summary tables, TEAEs will be counted as “Not Related” if relationship to study drug was recorded as ‘Not Related’ or “Unlikely”. Events will be counted as “Related” if relationship to study drug was recorded as ‘Possibly’, ‘Probably’, ‘Definitely’ or if relationship to study drug is missing.

Overviews of TEAEs will include total number of TEAEs and patient incidence of TEAE, TE SAE, related TEAE, related TE SAE, AESI, TEAE leading to withdrawal of IMP, Fatal TEAE. Individual TEAE summary will be presented by treatment group containing the following counts and percentages for:

- patients with TEAEs by SOC and PT
- patients with TEAEs by descending order of frequency of PT
- patients with treatment-related TEAEs by SOC and PT
- patients with treatment-related TEAEs by PT
- patients with TE SAEs by SOC and PT
- patients with TE SAEs by PT
- patients with treatment-related TE SAEs by SOC and PT

- withdrawal from study drug due to TEAEs by SOC and PT
- Fatal TEAEs by SOC and PT
- Patients with at least one AESI by AESI category and SOC and PT
- Patients with serious AESI by AESI category and SOC and PT

The AE overview summaries will count a patient at most once in each AE category (at the “highest/most extreme” designation of each category regardless of preferred term) and percentages will be based on the total number of patients in the safety population.

In addition to a comprehensive listing of all AEs (with non-TEAEs flagged), separate listings will be generated for AESIs, SAEs, AEs resulting in withdrawal of study drug, and AEs with a fatal outcome for safety population.

5.4.2 Adverse Events of Special Interest (AESIs)

AESIs include hepatic disorders (including increase from baseline in hepatic aminotransferases), musculoskeletal events (AE and CK evaluation), new onset diabetes/hyperglycemia, renal events, metabolic acidosis and/or hypoglycemia, and neurocognitive/neurologic events. The list of AESI terms is pre-defined by the Esperion and is included in Appendix 2.

- AESIs of muscle related symptoms will be summarized by treatment group. CK levels will be summarized by the value and change from baseline in the value, by treatment group and visit. In addition, the number and percent of patients with abnormal CK ($> 5 \times \text{ULN}$, $> 10 \times \text{ULN}$) values will be summarized. These summaries of patients with abnormal CK will be performed overall; by normal baseline CK; and by abnormal baseline CK.
- Cases of new onset of diabetes will be recorded as AEs and will be summarized using the appropriate SOC. These events will be summarized by severity, and relationship to study drug for each treatment group. Fasting glucose will be summarized at scheduled time point by history of diabetics.
- Neurocognitive events will be evaluated by routine safety monitoring of PE findings and AEs. Neurocognitive events will be identified using pre-specified MedDRA terms and will be summarized by SOC, severity, and relationship to IMP for each treatment group

AESI will be presented in a listing and summarized by AESI category, SOC, PT and treatment group.

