13.2.5. Reporting of Serious Adverse Events to Regulatory Authorities

The Sponsor (and/or designee) is responsible for submitting expedited reports of suspected and unexpected serious adverse reactions (SUSARS) to the appropriate regulatory authorities. All Investigators participating in ongoing clinical studies with the study drug will be notified by the Sponsor (or designee) of SUSARs. SUSARS must be communicated as soon as possible to the appropriate IRB/IEC by the investigator, as applicable and/or reported in accordance with local laws and regulations. Investigators should provide written documentation of IRB/IEC notification for each report to the Sponsor.

SAEs that are anticipated to occur in this patient population will be collected and reported by the Investigator as described in Section 13.2.4. However, these events will not be submitted to the

regulatory authorities as expedited reports unless they meet SUSAR criteria. These events that are considered to be exempt from expedited reporting include the following clinical endpoints:

- CV death;
- Nonfatal MI;
- Nonfatal stroke;
- Unstable angina requiring hospitalization;
- Coronary revascularization;
- Heart failure requiring hospitalization;
- Noncoronary arterial revascularization.

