13.3. Adverse Events of Special Interest

Adverse events of special interest (AESI) include metabolic acidosis (clinical laboratories), hepatic, muscular (AE and CK evaluation), new onset diabetes/hyperglycemia, renal, cardiovascular, and neurocognitive/neurologic events. Specific monitoring guidelines are provided in the case of AEs uncovered through laboratory evaluations.

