13.5. Clinical Event Committee (CEC)

A blinded independent expert Clinical Event Committee (CEC) responsible for adjudicating clinical endpoints including all major cardiovascular events from Phase 3 BA studies will be informed of this study and available for ad hoc review of specific data if needed. However, due to the study's relatively short enrollment period and treatment duration, the CEC will not routinely adjudicate clinical endpoints from this study.

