Appendix 2: AESI (Adverse Event of Special Interest)

AESI Category	Associated MedDRA Preferred Terms
Creatine kinase elevations	Blood creatine phosphokinase abnormal
Creatine kinase elevations	Blood creatine phosphokinase increased
Creatine kinase elevations	Blood creatine phosphokinase MM abnormal
Creatine kinase elevations	Blood creatine phosphokinase MM increased
New onset or worsening diabetes mellitus	Blood glucose abnormal
New onset or worsening diabetes mellitus	Blood glucose increased
New onset or worsening diabetes mellitus	Diabetes mellitus
New onset or worsening diabetes mellitus	Diabetes mellitus inadequate control
New onset or worsening diabetes mellitus	Diabetic ketoacidosis
New onset or worsening diabetes mellitus	Glucose tolerance impaired
New onset or worsening diabetes mellitus	Glucose urine present
New onset or worsening diabetes mellitus	Glycosuria
New onset or worsening diabetes mellitus	Glycosylated haemoglobin increased
New onset or worsening diabetes mellitus	Hyperglycaemia
New onset or worsening diabetes mellitus	Impaired fasting glucose
New onset or worsening diabetes mellitus	Ketoacidosis
New onset or worsening diabetes mellitus	Ketosuria
New onset or worsening diabetes mellitus	Ketosis
New onset or worsening diabetes mellitus	Type 2 diabetes mellitus
New onset or worsening diabetes mellitus	Urine ketone body present
Hepatic enzyme elevations	Alanine aminotransferase abnormal
Hepatic enzyme elevations	Alanine aminotransferase increased
Hepatic enzyme elevations	Aspartate aminotransferase abnormal
Hepatic enzyme elevations	Aspartate aminotransferase increased
Hepatic enzyme elevations	Blood bilirubin abnormal
Hepatic enzyme elevations	Blood bilirubin increased
Hepatic enzyme elevations	Hepatic enzyme abnormal
Hepatic enzyme elevations	Hepatic enzyme increased
Hepatic enzyme elevations	Hypertransaminaseaemia
Hepatic enzyme elevations	Liver function test abnormal
Hepatic enzyme elevations	Liver function test increased
Hepatic enzyme elevations	Transaminases abnormal
Hepatic enzyme elevations	Transaminases increased
Hypoglycemia	Blood glucose abnormal
Hypoglycemia	Blood glucose decreased
Hypoglycemia	Hypoglycaemia
Hypoglycemia	Hypoglycaemic coma
Hypoglycemia	Hypoglycaemic encephalopathy

AESI Category	Associated MedDRA Preferred Terms
Hypoglycemia	Hypoglycaemic seizure
Hypoglycemia	Shock hypoglycaemic
Metabolic acidosis	Metabolic acidosis
Muscular disorders	Muscular weakness
Muscular disorders	Muscle necrosis

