Muscular disorders	Muscle spasms
Muscular disorders	Myalgia
Muscular disorders	Myoglobin blood increased
Muscular disorders	Myoglobin blood present
Muscular disorders	Myoglobin urine present
Muscular disorders	Myoglobinaemia
Muscular disorders	Myoglininuria
Muscular disorders	Myopathy
Muscular disorders	Myopathy toxic
Muscular disorders	Necrotizing myositis
Muscular disorders	Pain in extremity
Muscular disorders	Rhabdomyolysis
Neurocognitive disorder	Amnesia
Neurocognitive disorder	Cognitive disorder
Neurocognitive disorder	Confusional state
Neurocognitive disorder	Disorientation
Neurocognitive disorder	Memory impairment
Neurocognitive disorder	Mental status changes
Renal disorders	Acute kidney injury
Renal disorders	Acute prerenal failure
Renal disorders	Blood creatinine abnormal
Renal disorders	Blood creatinine increased
Renal disorders	Blood urea abnormal
Renal disorders	Blood urea increased
Renal disorders	Blood urea nitrogen/Creatinine ratio increased
Renal disorders	Creatinine renal clearance abnormal
Renal disorders	Creatinine renal clearance decreased
Renal disorders	Glomerular filtration rate abnormal
Renal disorders	Glomerular filtration rate decreased
Renal disorders	Oliguria
Renal disorders	Prerenal failure
Renal disorders	Renal failure
Renal disorders	Renal function test abnormal
Renal disorders	Renal impairment
Gout	Gout

Addendum to Statistical Analysis Plan

Title: A Randomized, Double-Blind, Parallel Group Study to Evaluate the Efficacy and Safety of Bempedoic Acid 180 mg + Ezetimibe 10 mg Fixed Dose Combination Compared to Bempedoic Acid, Ezetimibe, and Placebo Alone in Patients Treated with Maximally Tolerated Statin Therapy.

Protocol: ETC-1002FDC-053

Clinical Phase: 3

Product: ETC-1002FDC

Date: Dec 24, 2018

Addendum to the Statistical Analysis Plan for Study 1002FDC-053

An Ad-hoc Sensitivity Analysis

Esperion completed the planned analysis as described in Study 1002FDC-053 SAP for all data collected in the study. During an in-depth review of the data, after unblinding, a data issue was identified that involved three sites. A formal investigation to assess the root cause of the data issue was launched. After review of the investigative results, the conclusion led us to question the data collected at three sites [REDACTED]

[REDACTED]

[REDACTED]

[REDACTED]

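### Cardiovascular events are AESI in the protocol but absent from the SAP's AESI list and Appendix 2, so the AESI outputs would omit them without explanation

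*SAP*

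**What the plan says.** Protocol 13.3 lists metabolic acidosis, hepatic and muscular events and then "new onset diabetes/hyperglycemia, renal, cardiovascular, and neurocognitive/neurologic events". The protocol synopsis commits to reporting AESI by treatment group. Protocol 14.8 commits to summarizing them by system organ class (SOC), severity and relationship.

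SAP 5.4.2 lists hepatic disorders and musculoskeletal events and then "new onset diabetes/hyperglycemia, renal events, metabolic acidosis and/or hypoglycemia, and neurocognitive/neurologic events". It continues: "The list of AESI terms is pre-defined by the Esperion and is included in Appendix 2". Appendix 2 is a table of AESI categories and MedDRA preferred terms (PT).

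SAP 5.4.1 plans an AESI line in the adverse event overview, a table described as "Patients with at least one AESI by AESI category and SOC and PT", the same table for serious AESI, and a separate AESI listing. SAP 5.4.3 repeats the AESI summary by subgroup. The first SAP addendum repeats an AESI table (T14.3.1.2.5) without the three questioned sites. Both documents say that the SAP prevails where the two differ on data analysis (Protocol 14.1, SAP 2).

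**The concern.** An AESI category exists so that a safety question fixed in advance gets its own grouped count by arm. Here the protocol fixed the cardiovascular area and the SAP, which controls the tables, has no such group. Every patient enters with ASCVD, HeFH and/or multiple cardiovascular risk factors, and characterizing safety is a secondary objective. Run as written, the AESI outputs would undercount AESI against the protocol's own definition. A reader of the study report who looks in the AESI table for cardiovascular events would find none and could take that as none observed.

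**Working it through.** No power, alpha or event figure bears on this point, and the plan states none to reproduce. The check sets the two AESI definitions side by side and reads Appendix 2 row by row.

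| AESI area in Protocol 13.3 | In SAP 5.4.2 | In SAP Appendix 2 (rows) |
|---|---|---|
| Metabolic acidosis | yes | Metabolic acidosis (1) |
| Hepatic | yes | Hepatic enzyme elevations (13) |
| Muscular, with CK | yes | Muscular disorders (14), CK elevations (4) |
| New onset diabetes/hyperglycemia | yes | Diabetes (16) |
| Renal | yes | Renal disorders (16) |
| Neurocognitive/neurologic | yes | Neurocognitive disorder (6) |
| **Cardiovascular** | **no** | **none (0)** |
| (not named) | Hypoglycemia | Hypoglycemia (7) |
| (not named) | (not named) | Gout (1) |

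1. Rows in Appendix 2: 1 + 13 + 14 + 4 + 16 + 16 + 6 + 7 + 1 = 78, in nine categories. None is cardiovascular. No row contains a term such as infarction, angina, stroke, heart failure or revascularization.
2. Areas carried over: 6 of 7. Cardiovascular is the only one dropped.
3. The set was otherwise extended. SAP 5.4.2 adds hypoglycemia, and Appendix 2 adds gout, which the text of 5.4.2 does not mention. So the list was revised, and the SAP's text and its own appendix do not fully agree.
4. The verb in SAP 5.4.2 is 'include', which could be read as non-exhaustive. The next sentence ties the terms to Appendix 2, so an event with no Appendix 2 term has no route into an AESI table.
5. The precedence clause settles which list is used. It does not say why an area was removed, and nothing else in the SAP does.
6. Addendum table T14.3.1.2.5 cites no other term list, so it appears to share the gap.
7. No other planned summary groups these events. SAP 5.4.4.1 to 5.4.4.4 cover hepatic, musculoskeletal, glycemic and renal safety. Protocol 14.8 covers those areas and neurocognitive events. Neither has a cardiovascular subsection.

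**The case against.** The strongest reply is that nothing is lost. SAP 5.4.1 plans counts by arm of treatment-emergent, serious and fatal adverse events by SOC and PT, with separate listings of serious and fatal events. Death and inpatient hospitalization are seriousness criteria, so most important cardiovascular events would appear there. This stands, and it limits the point to a missing grouping. It does not remove it: SOC and PT rows cannot be added to give patients with any cardiovascular event, because a patient with events in two rows would be counted twice.

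The removal may also have been deliberate, since the list is sponsor-defined and was revised elsewhere. That is possible, but then a reason is owed.

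A reader might infer more than the documents support:

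- *That cardiovascular events escape oversight.* Protocol 13.2.5 says "These events that are considered to be exempt from expedited reporting include the following clinical endpoints", and Protocol 13.5 says "the CEC will not routinely adjudicate clinical endpoints from this study". Protocol 13.4 adds that the DMC will not review the data on an ongoing basis. However, sites still report these events as SAEs within 24 hours, SUSARs are still expedited, and both committees remain available ad hoc. None of this determines which tables the SAP produces.
- *That the seven endpoints in Protocol 13.2.5 define the missing category.* That list serves expedited reporting, and Protocol 13.3 does not refer to it. A mapping by preferred terms alone would also fail. Protocol 13.1.3 records the condition behind a procedure as the adverse event, not the procedure, so the two revascularization endpoints would have no term of their own. Several others depend on hospitalization or fatal outcome.
- *That a material imbalance could be hidden.* The documents give no cardiovascular event rate. At a purely assumed 1% to 2% over 12 weeks, 350 × 0.01 to 0.02 = 3.5 to 7 patients in all: 1 to 2 per active arm of 100 and 0.5 to 1 on placebo. A grouped row would describe such counts but not support inference.

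**Conclusion.** The inconsistency is real: one of seven protocol-named AESI areas has no category and no term among 78 rows, and no reason is given. As written, the AESI overview count, the AESI and serious-AESI tables, the AESI listing and the AESI subgroup tables would omit cardiovascular events. For the addendum table this is an inference from its citing no other list. The consequence is limited to the absence of a grouped, patient-level cardiovascular count by arm in a descriptive safety analysis. No efficacy conclusion is affected. The conclusion rests on Appendix 2 being complete as published, and it shows no redaction. It does not depend on any assumed event rate.

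**What to change.** Add a 'Cardiovascular events' category to SAP 5.4.2 and Appendix 2:

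- Fix a list of preferred terms for the underlying conditions, for example myocardial infarction, unstable angina, stroke, heart failure and cardiovascular death.
- Where a term alone is not enough, use the seriousness and outcome fields that Protocol 13.1.3 already collects.
- Take revascularization from the underlying condition or from the concomitant-procedure data that SAP 5.2.8 lists, not from an adverse event term.
- Produce the AESI tables, the listing, the subgroup tables and T14.3.1.2.5 with this category.

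Both SAP addenda say that the planned analyses were complete and the data unblinded. A category added at that stage must be labelled post hoc, with its term list fixed before the counts by arm are tabulated. The second addendum already adds post hoc safety tables, so there is a route. If cardiovascular events were dropped on purpose, state the reason in the SAP and reconcile it with Protocol 13.3.

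The cost is a short derivation and some extra descriptive rows, with no new data collection. The drawback is that the rows will probably hold few events and can support description only.

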5.4.3 Subgroup Analysis for Adverse Events

The TEAE, related TEAE, TE SAE, and AESI summaries by SOC and PT will be provided for relevant subgroups described in 5.2.6 with the exception of baseline LDL

category.

5.4.4 Laboratory Evaluations

Continuous laboratory parameters (serum chemistry, hematology, coagulation for those who received anti-coagulation therapy patients), urinalysis, urinalysis [microscopic] listed in Table 4; and fasting glucose will be summarized using descriptive statistics for the observed value and the change/percent change from baseline at each protocol scheduled visits by history of diabetics. Missing values for any of the laboratory evaluations will not be imputed; that is, only observed case data will be used. Categorical urinalysis data will be provided in the listing.

As part of the AESI evaluation, below safety lab abnormality will be summarized by treatment group. All post-baseline lab values are being considered. Further details are provided in Section 5.4.4.1 through 5.4.4.4.

- ALT or AST (> 3x ULN and >5xULN)
- TB (> 2x ULN)
- Potential Hy's Law case: (ALT and/or AST > 3xULN with concurrent TB > 2xULN)
- CK (> 5x ULN) and (>10x ULN)
- Fasting Glucose (mg/dL) (≤ 50 , and ≥ 126) by history of diabetics
- Creatinine (change from baseline for >1 mg/dL)
- eGFR (< 15 mL/min/1.73m², 15 –< 30 mL/min/1.73m²)
- Hgb (g/dL) (decrease from baseline for ≥ 2 g/dL)
- Hgb (<8 g/dL)

Table 4: Clinical Laboratory Parameters (Safety)

Hematology	Blood Chemistry (serum, fasting)

 • Hematocrit (Hct) • Hemoglobin (Hgb) • Mean corpuscular hemoglobin (MCH) • Mean corpuscular hemoglobin concentration (MCHC) • Mean corpuscular volume (MCV) • Platelet count • Red blood (RBC) cell count • White blood (WBC) cell count with differential (absolute values only) 	
 • Albumin (ALb) • Alkaline phosphatase (ALk-P) • Alanine aminotransferase (ALT; SGPT) • Aspartate aminotransferase (AST; SGOT) • Blood urea nitrogen (BUN) • Calcium (Ca) • Carbon dioxide (CO₂) • Chloride (Cl) • Creatinine • Creatine kinase (CK) • Glucose • Lactate dehydrogenase (LDH) • Phosphorus • Potassium (K) • Sodium (Na) • Total and direct bilirubin (TB) • Total protein • Uric acid
Urinalysis (Dipstick)	Coagulation (In all patients at screening, then only in patients receiving anticoagulant therapy that in the investigator's judgment require monitoring at Visit T1 and 3 to 5 days post Visit T1)

 • Clarity • Bilirubin • Color • Glucose • Ketones • Leukocyte esterase • Nitrate • Occult blood • pH • Protein • Specific gravity • Urobilinogen 	
 • Prothrombin time • International normalized ration (INR)

Urinalysis (Microscopic)-only if urine dipstick abnormal

- Bacteria
- Casts
- Crystals
- Epithelial cells
- Red blood cell (RBC)
- WBC

The number and percentage of patients with laboratory abnormalities (i.e., laboratory values outside the stated laboratory normal range) will be summarized at each time point (i.e., including baseline and post-baseline time points) for each laboratory parameter by treatment groups. The determination of laboratory abnormalities will take into account any unscheduled laboratory assessments. Additional lab-related summaries will be provided as follows for hepatic safety, musculoskeletal safety, diabetes and hyperglycemia, and renal safety.

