7.3. Patient Lifestyle and Dietary Guidelines

Patients will fast for a minimum of 10 hours prior to collection of all laboratory samples (water and concomitant medications are permitted).

Beginning at screening, patients will be counseled to follow a heart healthy diet as per local or regional guidelines and should be encouraged (as able) to participate in a stable, regular exercise program throughout the study.

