11. ASSESSMENT OF EFFICACY

11.1. Assessments of Lipids and hs-CRP

Central clinical laboratory samples will be collected and analyzed for the parameters detailed in Table 3. LDL-C will be calculated or measured directly if TG are >400 mg/dL or LDL-C is <50 mg/dL.

Blood draws for lipids (not safety) must meet the criterion below. If this criterion has not been met, these blood samples will NOT be collected. **If this criterion can be met by rescheduling clinic visit to occur within 3 days, these blood samples will be collected at the rescheduled clinic visit only.**

- Blood samples will be drawn after a minimum 10-hour fast (water and concomitant medications are allowed)

Patients are to be in a seated position during the blood collection. Collection schedule and instructions are provided in the Central Clinical Laboratory Manual. A description of the sample collection, storage, and shipping as well as monitoring and management of abnormal laboratories are described in [Section 12.1.6](#).

When vital signs and laboratory samples are to be collected at the same time point, vital sign measurements will precede laboratory sample collection.

Table 3: Central Clinical Laboratory Parameters (Lipids and hs-CRP)

Clinical Laboratory Test	Clinical Laboratory Test
Basic Lipid Parameters 
• Total cholesterol (TC)• Calculated low-density lipoprotein cholesterol (LDL-C) and non-HDL-C• High-density lipoprotein cholesterol (HDL-C)• Triglycerides (TG)	Other Parameters 
• High-sensitivity C-reactive protein (hs-CRP)• Apolipoprotein B (ApoB)

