Patients will be in a seated position during the blood collection. Clinical laboratory parameters and tests will include those listed in [Table 4](#). Collection schedule, schedule of laboratory parameters by visit, and instructions are in the Clinical Laboratory Manual provided by Central Laboratory.

Table 4: Central Clinical Laboratory Parameters (Safety)

Clinical Laboratory Test	Clinical Laboratory Test
Hematology 
• Hematocrit (Hct)• Hemoglobin (Hgb)• Mean corpuscular hemoglobin (MCH)• Mean corpuscular hemoglobin concentration (MCHC)• Mean corpuscular volume (MCV)• Platelet count• Red blood (RBC) cell count• White blood (WBC) cell count with differential (absolute values only)	Blood Chemistry (serum, fasting) 
• Albumin (ALB)• Alkaline phosphatase (ALK-P)• Alanine aminotransferase (ALT; SGPT)• Aspartate aminotransferase (AST; SGOT)• Blood urea nitrogen (BUN)• Calcium (Ca)• Carbon dioxide (CO₂)• Chloride (Cl)• Creatinine• Creatine kinase (CK)• Glucose• Lactate dehydrogenase (LDH)• Phosphorus• Potassium (K)• Sodium (Na)• Total and direct bilirubin (TB)• Total protein• Uric acid
Urinalysis (Dipstick) 
• Clarity• Bilirubin• Color• Glucose• Ketones• Leukocyte esterase• Nitrite• Occult blood• pH• Protein• Specific gravity• Urobilinogen	
Urinalysis (Microscopic) – only if urine dipstick abnormal 
• Bacteria• Casts• Crystals• Epithelial cells• Red blood cells (RBC)• White blood cells (WBC)	Coagulation – ONLY in patients receiving anticoagulant therapy that in the investigator's judgment requires monitoring, measured only at Visit T1 and 3 to 5 days post Visit T1 
• Prothrombin time (PT)• International normalized ratio (INR)

Table 4: Central Clinical Laboratory Parameters (Safety)

Clinical Laboratory Test	Clinical Laboratory Test
Other Screening Labs 
• Hepatitis B surface antigen (HBsAg), hepatitis C virus (HCV), optional reflexive hepatitis C RNA only if HCV is positive• Serum and urine pregnancy test (only for females of childbearing potential)• Follicle-stimulating hormone (FSH; only for postmenopausal females <55 years old >1 year without menses)• Thyroid-stimulating hormone (TSH)	Other Sample Collection 
• Plasma trough investigational medicinal product (IMP)

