12.1.6.4.2. Monitoring and Management of Elevated Creatine Kinase

If at any time after randomization a patient experiences a marked CK elevation $>5 \times$ ULN, the patient will undergo repeat confirmatory assessment as soon as is reasonably possible, preferably within 3 to 7 days of the laboratory result becoming available. If initial CK elevation is $>10 \times$ ULN, patients will be instructed to discontinue IMP immediately (instead of continuing IMP until repeat lab value is assessed). It is very important that repeat confirmatory assessment occur as soon as possible (within a day of stopping IMP).

Repeat CK assessment will include query for the nature, duration and intensity of any muscle symptoms; review possible predisposing factors, such as unaccustomed exercise, heavy alcohol intake, viral illness (consider performing serology), concomitant medications, and/or other conditions which can cause myopathy; physical examination for muscle tenderness, weakness, and rash; measure serum creatinine, dipstick urinalysis \pm microscopy if indicated; and basic metabolic panel.

- If the repeat CK assessment confirms an unexplained (ie, not associated with recent trauma or physically strenuous activity) CK abnormality $>5 \times$ ULN, if asymptomatic the patient should receive further assessment and investigation into the cause, assess whether there is renal injury and measure CK approximately weekly or more frequently if clinically indicated until resolution. If CK levels continue to rise; IMP should be discontinued.
- If the repeat CK assessment confirms an unexplained (i.e., not associated with recent trauma or physically strenuous activity) CK abnormality as listed below, the patient should discontinue IMP:
 - $>5 \times$ ULN that is associated with symptoms of muscle pain, muscle weakness, or dark urine; or
 - $>10 \times$ ULN, even in the absence of symptoms.
- At the investigator's discretion, IMP may be interrupted and the patient rechallenged with IMP after CK has returned to the baseline level.

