5.4.4.3 Diabetes and Glycemia

For fasting serum glucose, a shift table from baseline with the number and percent of patients will be categorized as below:

Fasting glucose: $\geq 126 \text{ mg/dL}$; $100-125 \text{ mg/dL}$, and $< 100 \text{ mg/dL}$. These tables will be summarized by history of Diabetes.

Descriptive summary for fasting serum glucose will be provided by history of diabetics and treatment group at each scheduled visit.

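### Fasting is enforced only for lipid draws, but the SAP applies fasting glucose cut-offs to all post-baseline values without a check of fasting status

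*SAP*

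**What the plan says.** **Fasting rules.** Protocol 7.3 is general: "Patients will fast for a minimum of 10 hours prior to collection of all laboratory samples". The Synopsis, Protocol Table 4 and SAP Table 4 all label the chemistry panel, which contains glucose, as a fasting panel. Protocol 11.1 is narrower: "Blood draws for lipids (not safety) must meet the criterion below". The criterion is the 10-hour fast, and the consequence falls on the lipid tubes alone: "If this criterion has not been met, these blood samples will NOT be collected". They may be taken at a visit rescheduled within 3 days. Nothing withholds or moves the chemistry sample.

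**Analysis rules.** SAP 5.4.4 introduces its list of laboratory abnormalities with "All post-baseline lab values are being considered". The list includes fasting glucose <=50 and >=126 mg/dL, split by history of diabetes. SAP 5.4.4 also brings unscheduled assessments into the out-of-range counts. SAP 5.4.4.3 adds: "For fasting serum glucose, a shift table from baseline with the number and percent of patients will be categorized as below", with bands >=126, 100-125 and <100 mg/dL. Under SAP 5.2.2, baseline for these laboratory values is the last non-missing value before first dose, with no fasting condition.

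**Other glycaemic measures.** The schedule of events places HbA1c at screening only. Dipstick glucose and ketones are part of the on-treatment urinalysis, but SAP 5.4.4 sends categorical urinalysis results to a listing.

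**The concern.** Protocol 11.1 foresees a patient who arrives without having fasted and lets the safety blood go ahead. The SAP then grades glucose against thresholds that mean what they say only in a fasted patient. Because any post-baseline value can count, one fed sample is enough to put a patient in the >=126 mg/dL row. The shift table is exposed at both ends: a fed post-baseline value can create a false upward shift, and a fed baseline value can hide a real one.

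New-onset diabetes/hyperglycaemia is an adverse event of special interest, and serum glucose is the only blood measure of glycaemia scheduled after randomisation. The laboratory-abnormality tables are also among the outputs that both SAP addenda return to (T14.3.5.1a, and Tables 17.4.1.1.1 to 17.4.1.1.3).

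**Working it through.** The plan states no figure on this point, so there is none to reproduce. The check has two parts: the text, then an illustration of size.

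**1. Can an unfasted glucose enter the tables?**

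- Collection: 7.3 tells the patient to fast for all blood. 11.1 attaches a consequence to a missed fast for lipids only. An unfasted chemistry sample departs from 7.3, but nothing stops it being drawn.
- Analysis: neither SAP 5.4.4 nor 5.4.4.3 identifies, flags or excludes such a sample. The word fasting does not filter, because the panel carries that label whether or not the patient fasted.
- Comparison: where sampling conditions matter elsewhere, the documents say so. SAP 5.2.1.4 leaves PK samples outside 18 to 30 hours after dosing out of the summary. Protocol 12.1.6.4.3 asks for at least a 10-hour fast before a repeat triglyceride test. Glucose has no equivalent rule.

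So an unfasted glucose can enter.

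**2. How many patients might be affected?**

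Input from the documents: three scheduled on-treatment draws (Weeks 4, 8 and 12). Assumed inputs: *u*, the share of safety draws taken unfasted, 1% to 5%; *q*, the chance that an unfasted value is >=126 mg/dL when a fasted one would not be, 10% to 30%.

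Patients with at least one unfasted on-treatment draw = 1 - (1 - *u*)^3:

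- *u* = 1%: 1 - 0.99^3 = 3.0%
- *u* = 3%: 1 - 0.97^3 = 8.7%
- *u* = 5%: 1 - 0.95^3 = 14.3%

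False flags per 100 patients = that share x *q*:

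- Low: 3.0 x 0.10 = 0.3
- High: 14.3 x 0.30 = 4.3

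Counting each draw separately, 1 - (1 - *uq*)^3 gives almost the same: 1 - 0.999^3 = 0.3% and 1 - 0.985^3 = 4.4%. With wider assumptions (*u* up to 10%, *q* up to 40%) the upper end is 1 - 0.96^3 = 11.5%.

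**3. What does that do to a comparison between arms?**

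Suppose the false-flag rate *f* is the same in every arm, and the true rates are 15% and 5% (assumed; ratio 3.0). The observed rates are 0.15 + 0.85*f* and 0.05 + 0.95*f*.

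| *u*, *q* | *f* | Observed rates | Ratio |
|---|---|---|---|
| 1%, 10% | 0.3% | 15.25% vs 5.28% | 2.89 |
| 5%, 20% | 3.0% | 17.5% vs 7.8% | 2.24 |
| 10%, 40% | 11.5% | 24.8% vs 15.95% | 1.55 |

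Equal misclassification pulls the ratio towards 1. It does not create a difference.

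**The case against.** The best defence is that the SAP names its variable fasting glucose in 5.4.2, 5.4.4 and 5.4.4.3. On that view the sentence about all post-baseline values is a generic lead-in to a list of nine rows, and an unfasted sample was never meant to be included. Protocol 7.3 also makes fasting the rule for all blood. This stands in part: the documents do not say that unfasted values are to be graded, only that nothing removes them. It is therefore right to say they may be counted, not that they will be.

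Four stronger readings are tempting, and the documents do not support them.

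- *Safety blood is exempt from fasting.* It is not; 7.3 and the panel label cover it. It is exempt only from the withhold-or-reschedule rule in 11.1.
- *Repeat draws after liver or CK elevations bias the comparison between arms.* The liver repeat panel in Protocol 12.1.6.4.1 contains no glucose. The CK work-up ends with "and basic metabolic panel", but the protocol does not list that panel's contents, nothing shows how often it would be drawn, and 7.3 makes no exception for repeats. In a double-blind trial, missed fasts at scheduled visits should be about equally common in each arm.
- *A false flag is a false case of new-onset diabetes.* Events of special interest are identified from the preferred terms in SAP Appendix 2. A laboratory value is not itself such an event.
- *Glucose is the only on-treatment glycaemic laboratory measure.* It is the only scheduled blood measure; urine glucose and ketones are also collected.

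Finally, the case report form and laboratory manual are not among the documents and may already record fasting status. That would make the fix easier, but the SAP would still need to say that the field is used.

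**Conclusion.** The concern holds as a gap between collection and analysis. Protocol 7.3 and 11.1 are not aligned, and the SAP applies fasting thresholds, at baseline and afterwards, without a fasting-status rule. Some glucose values may be misclassified as hyperglycaemia or may distort the shift table.

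The size is uncertain and probably modest: about 0.3 to 4 falsely flagged patients per 100, resting wholly on the assumed 1-5% unfasted draws and 10-30% exceedance, before any unscheduled samples. The expected effect is non-differential noise and dilution. A reader might infer bias against one arm, but the documents do not show it. SAP 5.4 makes all safety output descriptive, so no test or success criterion depends on these tables. This is a cheap improvement to a safety display, not a threat to the trial's conclusions.

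**What to change.** 1. **Protocol:** reconcile 7.3 and the fasting label in Table 4 with the wording of 11.1, so that it is clear what happens to a chemistry sample when the patient has not fasted.
2. **Data collection:** record fasting status (at least 10 hours, yes/no) with each chemistry draw, scheduled or unscheduled, if the eCRF or laboratory manual does not already do so.
3. **SAP 5.4.4 and 5.4.4.3:** restrict the >=126 mg/dL row and the shift table, including its baseline, to samples confirmed as fasted. List glucose of unfasted or unknown status separately. Keep the <=50 mg/dL row on all samples.
4. **Where status is missing:** treat a lipid result from the same draw as evidence of fasting, since 11.1 bars unfasted lipid draws. Match on the draw, not the visit, because rescheduled lipids can come up to 3 days after the chemistry sample.

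The cost is at most one data field and a sentence or two in the SAP, with no new sample. The downside is that a few glucose values leave the hyperglycaemia tables. The SAP addenda say that the planned analyses have been run; for data already collected without a fasting field, the proxy in step 4 allows the tables to be rerun as a supplement.
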